Participants may be inconvenienced by taking part in components of the study (e.g., exit interviews). The COVID-19 pandemic is also a stressful situation to many; therefore, risks will be mitigated by ensuring participants are aware that they have the option to participate and/or not answer any questions they do not wish to answer. Participants will be able to withdraw from the study at any point with no consequences by notifying a study coordinator, investigator or the resource navigator. Participants may have to withdraw due to end of employment or personal concerns. Preliminary sample size estimations have been calculated to account for participant attrition.

11c. Adherence

To facilitate adherence to the intervention, participants in the intervention arm will receive a package that includes educational resources by email and/or mail each month. Resource navigators will directly reach out to participants in the intervention arm (via email/phone) and will provide them with two hours of navigation support sessions (by phone/zoom) per month for six months. Additionally, during the course of the intervention, the resource navigation will also identify processes to enhance adherence for the six-month period through various methods including personalization of sessions (participant's communication and time preference) and providing ambient information pre-session (session reminders, goal of each session).

11d. Concomitant Care

Due to the nature of this study, all participants will be assessed if they are receiving other interventions related to wellness, which can be self-directed or organization directed. This will also enable the identification co-intervention bias, which can impact on the study outcome

12. Outcome Measures

1. Primary Outcome Measures

The primary outcome for this study is the impact of the intervention on staff wellness. This will be measured by determining the impact of resource navigation on the change in wellness between the 6-month time point and baseline for those who received educational resources and resource navigation compared to those who received educational resources alone.

Participant wellness will be assessed using the Personal Wellbeing Score.[31] The Personal Wellbeing Score measure was selected to align with the World Health Organization's 2004

Evaluating the impact of resource navigators to support long-term care and retirement home staff during and beyond COVID-19

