Principal Investigators: Drs. [name] and [name]

Research ethics protocol

Version Dates: Sept 7th, 2022

Version Number: 2

definition of wellness: “the optimal state of health of individuals and groups. There are two focal concerns: the realization of the fullest potential of an individual physically, psychologically, socially, spiritually, and economically, and the fulfilment of one’s role expectations in the family, community, place of worship, workplace and other settings.” p.5, World Health Organization [32]

The Personal Wellbeing Score is a short, 4-item measure that takes a few minutes to complete. These features increase accessibility and reduce participant burden compared to longer wellness assessment tools. The scale has good internal reliability (Cronbach’s $\alpha = 0.90$) and correlates with health status ($r=0.58$) and health confidence ($r=0.60$). [31] The analysis will use mean Personal Wellbeing Scores of participants and will be conducted at baseline and 6-months post-intervention.

2. Secondary Outcome Measures

Secondary outcome measures will include burnout, knowledge, access to and use of wellness supports, vaccination status, SARS-CoV-2 infection, hospitalization, and death. All measures will be assessed through a baseline and exit survey (at the 6-month time point) that includes the Personal Wellbeing Score.

Burnout will be assessed with the 22-item Maslach Burnout Inventory for Medical Personnel. [33] This measure takes approximately 10 minutes to complete, demonstrates good reliability and validity, has been tested among diverse stakeholder populations including PSWs, and tests for relevant domains (e.g., emotional exhaustion). [33-36] To assess knowledge, access to and use of wellness supports, Likert scale questions directly related to outcomes will be developed.

Demographic information will also be collected, and questions will be developed using the PROGRESS-Plus framework. [37] The PROGRESS-Plus framework will assess characteristics such as place of residence, race/ethnicity/culture/ language, occupation, gender, sex, religion, education, socioeconomic status, and social capital) to determine effects on the study outcomes.

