Via participants’ Ontario Health Insurance Plan (OHIP) number, we will link to the ICES provincial administrative database to obtain participants’ vaccine status, and rates of SARS-CoV-2 infection, hospitalization and death, over the study period. [38, 39]. Unique to the exit survey, study participants will be asked about their satisfaction with the intervention. A process evaluation will be conducted to assess quality and delivery of the study intervention. The resource navigator will track the number, duration and focus of the 1:1 sessions per participant at the end of each individual session using a Process Evaluation- Intervention Tracking Form (Appendix Q). Participant experiences, suggestions for improvement and planning for sustainability will be collected via individual interviews with the resource navigator. A sample of

Evaluating the impact of resource navigators to support long-term care and retirement home staff during and beyond COVID-19

Principal Investigators: Drs. [name] and [name]

Research ethics protocol

Version Dates: Sept 7th, 2022

Version Number: 2

control (n=8-10) and intervention (n=8-10) participants will be interviewed. We will purposively sample the group, with an aim to reflect diversity in gender, age, race and other PROGRESS-plus characteristics

13. Participant Timeline

As noted above, the primary and secondary outcomes will be assessed using a multi-measure baseline and exit survey. Baseline surveys will be conducted 0-30 days after randomization and exit surveys will be conducted at 6 months (182 days) after the randomization date.

Process evaluation data will be collected throughout the duration of the intervention (from 0 days after randomization until the end of intervention (182 days)).

Post-intervention exit interviews will then be conducted at approximately 6-7 months (182-213 days) after the randomization date. These interviews will include a subsample of 8-10 participants from the intervention arm and 8-10 participants from the control arm of the study. See Figure 1 for flow of participants. Note: this will be a rolling recruitment.

Evaluating the impact of resource navigators to support long-term care and retirement home staff during and beyond COVID-19

[figure not shown]
Principal Investigators: Drs. [name] and [name]

Research ethics protocol

Version Dates: Sept 7th, 2022

Version Number: 2

Figure 1. Flow of Participants

14. Sample Size

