This study estimates that the standard deviation (SD) across mean Personal Wellbeing Scores is 10.2.[31] Assuming we will use a t-test to compare the scores across the intervention groups, a medium effect size of 0.5, a SD estimate of 10.2, a false positive error rate of 5% and a power of 80%, the estimated sample size is 64 participants per arm or 128 for the two arms. Including a buffer for participation attrition of 20%, the study will require a total of 154 participants (77 per arm).

Evaluating the impact of resource navigators to support long-term care and retirement home staff during and beyond COVID-19

Principal Investigators: Drs. [name] and [name]

Research ethics protocol

Version Dates: Sept 7th, 2022

Version Number: 2

15. Recruitment

The study team will be using multiple recruitment strategies: circle of contacts, snowball, and advertisements (Appendix A, B, Y). The study team will also leverage partnerships with OPSWA, Ontario LTC Association (OLTCA), Family Councils Ontario (FCO), and other Long Term Care and retirement organizations to recruit PSWs and other service support staff working in Ontario long-term care and retirement homes. All interested potential participants will be provided with a pre-screening survey to determine eligibility, the study information sheet and a consent form..

Methods: Assignment of Interventions (for controlled trials)

16. Allocation

16a. Sequence Generation

Participants will be randomly assigned to either control or intervention group with a 1:1 allocation sequence using computer software and will use block randomization with randomly selected block sizes to keep the enrollment sizes in each arm similar throughout the trial. [40] This will be done under the supervision of the study statistician (BP).

16b. Concealment Mechanism

The study team will use a secure web application called Research Electronic Data Capture (REDCap) to randomly allocate participants to the intervention and control arms, which will conceal the sequence and allocation until the point of assignment. [40]

16c. Implementation

All participants who provide consent for participation and who fulfil the inclusion criteria will be randomized. A statistician from the study team will generate the random allocation sequence. Research coordinators of the study will enroll participants and assign them to a study arm (control or intervention arm).

17. Blinding

17a. Blinding (Masking)

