Due to the nature of the intervention, neither participants nor researchers will be blinded to the study arm; however, statisticians conducting the outcome analysis will be blinded to which arm participants were assigned. PSWs and other support service staff in the same long-term care and retirement home may be randomized to different study arms, which may cause contamination; however, this is unlikely since those in the control arm will not have access to the navigators.

Evaluating the impact of resource navigators to support long-term care and retirement home staff during and beyond COVID-19

Principal Investigators: Drs. [name] and [name]

Research ethics protocol

Version Dates: Sept 7th, 2022

Version Number: 2

17b. Emergency Unblinding

Since direct study participants and researchers will not be blinded throughout the duration of the study, unblinding procedures will not be required or necessary for the purposes of this trial

Methods: Data collection, management, and analysis

18. Data Collection Methods

18a. Data Collection Methods

Data will be collected by the Knowledge Translation Program, Li Ka Shing Knowledge Institute, Unity Health Toronto (KTP-UHT). Baseline and exit surveys will be administered online via REDCap.

The study will use the Dillman Total Design Method (follow up at 1, 3, 7, 10 weeks) to increase survey responsiveness. [40] Participants who indicate interest and meet study criteria will be asked to complete a baseline survey at the beginning of the study (0 weeks). If they do not respond immediately, they will receive reminder emails at 1, 3, 7 and 10 weeks. At the 6-month mark, after study completion (26 weeks), participants will be asked to complete an exit survey. If they do not respond immediately, they will also receive reminder emails at 1, 3, 7 and 10 weeks. However, based on whether there are delays in the ability to recruit participants due to a lack of response to recruitment emails and reminders, there is a possibility that the surveys will not take place at the exact times noted above. If this occurs, we will make sure to note this in our limitations. All survey questions have been reviewed by the steering committee for acceptability, clarity of language and feasibility of format (e.g., mobile friendly access).

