We will use descriptive statistics to report participant demographics and study outcomes. We will use t-tests to compare outcomes for the intervention and control groups. We will disaggregate data by sex, gender, age, long-term and retirement home staff type, and long-term care home type (e.g., for-profit, municipally owned). Where possible (for cells with $n \geq 5$), we will disaggregate data by other PROGRESS-Plus demographics, in line with an intersectionality-based approach. [31, 37, 44-45, 48].

20b. Additional Analysis

There is no additional analysis that has been identified for this research study.

20c. Analysis Population and Missing Data

Evaluating the impact of resource navigators to support long-term care and retirement home staff during and beyond COVID-19

Principal Investigators: Drs. [name] and [name]

Research ethics protocol

Version Dates: Sept 7th, 2022

Version Number: 2

The analysis of the population, as earlier identified, includes a t-test for the comparison of both the control and intervention groups, and also qualitative analysis with the use of NVivo. All questions are optional and participants can skip questions they do not feel comfortable answering. We will consult with a study statistician to develop a plan for missing data.

Methods: Monitoring

21. Data Monitoring

21a. Formal Committee & (b) Interim Analysis

Due to the length and minimal risks associated with the study, a Data Monitoring Committee and interim analysis will not be required. Data will be monitored throughout the duration of the study by the Research Coordinator and Research Assistant in accordance with the Unity Health Toronto Institutional Review Board guidance and standards. The Research Ethics Board may request to review the study records for monitoring purposes.

22. Harms

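### The primary comparison is an unadjusted t-test on an unsettled variable; prespecify regression of the 6-month score on a baseline taken before allocation

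*Combined protocol and SAP*

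**What the plan says.** Section 20a gives the whole between-arm analysis: "We will use t-tests to compare outcomes for the intervention and control groups". Section 20c repeats the t-test, Section 20b says no further analysis is identified, and no covariate-adjusted model appears anywhere.

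The variable to be tested is described in different ways:

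- Section 12 (primary outcome) defines it as "the change in wellness between the 6-month time point and baseline", then adds: "The analysis will use mean Personal Wellbeing Scores of participants and will be conducted at baseline and 6-months post-intervention".
- Section 14 uses scores: "Assuming we will use a t-test to compare the scores across the intervention groups, a medium effect size of 0.5". The SD is also one of scores: "the standard deviation (SD) across mean Personal Wellbeing Scores is 10.2".
- Section 20a says only that outcomes are compared.

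On the timing of baseline:

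- Section 13: "Baseline surveys will be conducted 0-30 days after randomization".
- Section 16c: "All participants who provide consent for participation and who fulfil the inclusion criteria will be randomized". Completing the baseline survey is not a condition.
- Section 18a sends reminders to baseline non-responders at weeks 1, 3, 7 and 10. The last two fall on days 49 and 70, outside the 30-day window.
- Section 26a is unclear on order. It emails the baseline link after consent, then lists assignment to an arm ahead of the baseline invitation.
- Section 17a: "neither participants nor researchers will be blinded to the study arm".

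**The concern.** Two statisticians following this plan could report different primary results, one testing 6-month scores and the other testing change. If baseline is free of treatment effect and the SDs at the two times are equal, both tests and regression on baseline target the same mean difference. They differ in precision. Regression has the smallest residual variance whenever the correlation r between baseline and 6 months lies strictly between 0 and 1, and it also corrects chance imbalance at baseline.

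The timing matters because the outcome is self-reported and participants know their arm. A baseline answered after allocation, possibly after navigation has begun, may already contain part of the effect. A change score subtracts all of that part; regression subtracts a fraction of about r.

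**Working it through.** **Inputs.** From Section 14: SD of scores 10.2, effect size 0.5, error rate 5%, power 80%, 64 per arm before attrition. Target difference: 0.5 × 10.2 = 5.1 points. Assumed here: a two-sided test (the plan does not say), equal SDs at both times, and r. The documents give neither r nor an SD of change.

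**The plan's figure.** The exact two-sample t calculation for d = 0.5 gives 63.77, so 64 per arm, which matches. A one-sided test would need 51. Power at 64 per arm is 80.15%.

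**Three analyses of the same data.** Noncentral-t power with noncentrality (5.1 / SD) × √(64/2), where the SD is:

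- 6-month score: 10.2, with 126 df
- change: 10.2 × √(2(1 − r)), with 126 df
- regression on baseline: 10.2 × √(1 − r²), with 125 df

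At r = 0.3, for example, these SDs are 10.2, 12.07 and 9.73.

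| r (assumed) | Score: power | Change: power | Regression: power | Pairs per arm for 80% (score / change / regression) |
|---|---|---|---|---|
| 0.2 | 80.1% | 60.2% | 81.7% | 64 / 102 / 62 |
| 0.3 | 80.1% | 66.0% | 83.7% | 64 / 89 / 59 |
| 0.5 | 80.1% | 80.1% | 90.0% | 64 / 64 / 49 |
| 0.7 | 80.1% | 95.2% | 97.6% | 64 / 39 / 34 |

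Change reaches 80% only from r of about 0.5, unless the 0.5 was meant in units of the SD of change; then it reaches 80% at any r. At r = 0 regression has 80.1%.

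**After the plan's own attrition.** 77 × 0.8 = 61.6, so 61 completers per arm. The score t-test then has 78.2%. At r = 0.3, 0.5 and 0.7 change has 63.9%, 78.2% and 94.3%, and regression 81.9%, 88.5% and 97.0%.

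**Baseline after allocation.** Assume the effect accrues linearly over 182 days and the whole intervention arm answers on day 30. The baseline shift is s = 5.1 × 30/182 = 0.84 points. Change then estimates 5.1 − s and regression 5.1 − r·s. With 64 per arm:

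| r (assumed) | Change: estimate, power | Regression: estimate, power |
|---|---|---|
| 0.3 | 4.26 (16% low), 51% | 4.85 (5% low), 79.9% |
| 0.5 | 4.26 (16% low), 65% | 4.68 (8% low), 84.5% |
| 0.7 | 4.26 (16% low), 86% | 4.51 (12% low), 93.5% |

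Regression falls below the score t-test's 80.1% once s exceeds 0.78, 1.37 or 2.08 points at these values of r. The assumed 0.84 just passes the first of these, costing about 0.3 percentage points of power.

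**Missing baselines.** Simulation with 64 per arm, an assumed 2% or 5% of baselines missing completely at random, and 10,000 trials per setting. Complete-case regression has 82.4% or 80.9% power at r = 0.3, and 89.4% or 88.6% at r = 0.5. Filling with the overall mean plus an indicator gives 82.9% or 82.7%, and 89.8% or 89.7%.

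**The case against.** **Baseline is already used.** Section 12 defines the outcome as change, so the t-test is most naturally one on change and baseline enters by subtraction. That is a fair reading, but Section 14 does not follow it. Subtraction is also less precise than regression under equal SDs, and below r = 0.5 it is less precise than ignoring baseline.

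**The gain may be small.** Against a t-test on 6-month scores, regression adds only 1.6 points of power at r = 0.2, and r is unknown. This stands. The case for regression is that it costs almost nothing if r is low: allowing for estimation of the baseline slope, power at r = 0 is 79.8% instead of 80.1%.

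**The timing evidence is mixed.** The project timeline puts the baseline survey in June-July 2022 and the intervention from August-September. However, it puts assignment in the same June-July column, so it does not place baseline before allocation, and Section 13 says recruitment is rolling. The 0.84-point shift is near the upper end for the 30-day window under linear accrual; answers averaging day 15 would halve it to 0.42. A reaction to learning one's arm is not modelled.

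**The unadjusted fallback can be disputed.** With the 0.84 shift, root-mean-square error for regression is 1.74, 1.62 and 1.42 at r = 0.3, 0.5 and 0.7, against 10.2 × √(2/64) = 1.80 for the unadjusted score. Preferring the unadjusted comparison when baseline stays after allocation therefore puts freedom from bias ahead of total error. That is a judgement.

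**Conclusion.** The concern holds. The plan does not fix the analysed variable, uses no covariate adjustment although baseline is collected, and schedules baseline after allocation in an unblinded trial with a self-reported outcome. The t-test is not invalid and no power shortfall is demonstrated.

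With a baseline free of treatment effect, equal SDs and a 5.1-point difference, regression gains 1.6 to 17.5 percentage points over a 6-month-score t-test as r runs from 0.2 to 0.7. Over a change t-test it gains 21.5 points at r = 0.2 and 2.4 at r = 0.7. These sizes depend on an assumed r. The preference for regression over both t-tests does not, for any r clearly above zero. This is a change the plan should make, using data it already collects.

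**What to change.** 1. **Section 20a.** State that the primary analysis is a linear regression of the 6-month Personal Wellbeing Score on arm and baseline score, reporting the adjusted mean difference with its 95% CI. Use the same model for other scale outcomes measured at both times, after checking that it suits the Likert items still to be developed. With baseline as covariate, the arm coefficient is identical if change is the dependent variable, so Section 12's outcome is respected.
2. **Sections 13, 16c, 18a and 26a.** Have the baseline survey completed after consent and before allocation, and define completed, since questions are optional. If the order cannot change, make the unadjusted 6-month score comparison primary, amend Section 12 to match, and show the adjusted result as a sensitivity analysis.
3. **Section 20c.** State how a remaining missing baseline is handled (for example, overall baseline mean plus a missing indicator) so that no randomised participant with a 6-month score is dropped. State how a partly answered 4-item score is treated.
4. **Sections 12 and 14.** Use this one endpoint throughout, say that 10.2 is the SD of scores, give the target difference in points, and show power over a range of r.

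**Cost.** Wording in eight sections (12, 13, 14, 16c, 18a, 20a, 20c and 26a) and an amendment communicated under Section 25. Allocation would wait for the survey, so enrolment may slow and some people who consent may never be randomised. No new data items are needed.

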These barriers were mapped to corresponding implementation strategies via the Behaviour Change Wheel framework to identify education and enablement (e.g., supporting individuals' own self-efficacy) as interventions to mitigate the identified barriers.[13] Utility of these interventions was confirmed by our long-term care home staff partners and the Ontario PSW Association (OPSWA, who support >50,000 members), who believed routine check in calls

Evaluating the impact of resource navigators to support long-term care and retirement home staff during and beyond COVID-19

Principal Investigators: Drs. [name] and [name]

Research ethics protocol

Version Dates: Sept 7th, 2022

Version Number: 2

would reduce social isolation and support PSWs and other long-term care staff to find and use available resources to address their needs.[13]

Through funding from the COVID-19 Immunity Task Force (CITF), the Ontario Ministry of Labour Training and Skills Development (MOLTSD) and the Canadian Immunization Research Network (CIRN), the KTP developed educational resources compiled in a single online repository for long-term care home staff on optimizing infection prevention and control (IPAC) [14-17] in long-term care home, promoting wellness and preventing burnout [18,19] providing ‘wraparound’ [20, 21] resource supports to individuals (e.g., access to food banks, resources on self-isolation, caring for a family member with COVID-19), and addressing SARS-CoV-2 vaccine [22-24] myths and questions (via infographics and town halls created in partnership with OPSWA).[25, 26]

However, currently long-term care and retirement home staff access these resources passively and many do not have the capacity or skills to implement the resources effectively. A navigator is the missing link to putting these resources into practice.

Research Question

Through this clinical trial, we aim to answer the following research question:

What is the impact of tailored 1:1 support from a resource navigator and educational resources (intervention arm) compared to educational resources only (control arm) on the wellness of long-term care and retirement home staff (primary outcome), burnout, knowledge of, access to and use of wellness resources, SARS-CoV-2 vaccination status, self-reported SARS-CoV-2 infection and hospitalization (secondary outcomes).

6b. Choice of Comparators

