Exit Survey	
 • Outcome evaluation • Demographic information 	
 • up to 154 participants (77 per arm) 	
 • At 6 months, Study coordinator and Assistant will collect Exit Survey data after completion of intervention 	
 • Wellbeing • PROGRESS-Plus factors (gender, sex, religion, education, socioeconomic status, and social capital) • Knowledge • Access to supports • Use of wellness supports • Satisfaction with the intervention 	
 • Personal Wellbeing Score (Primary Outcome) • Demographic questionnaire-PROGRESS-Plus Framework and OHIP number (if not collected at baseline) • Maslach Burnout Inventory • Likert scale questions evaluating knowledge, access to and use

Evaluating the impact of resource navigators to support long-term care and retirement home staff during and beyond COVID-19

Principal Investigators: Drs. [name] and [name]

Research ethics protocol

Version Dates: Sept 7th, 2022

Version Number: 2

					of wellness supports
Exit Interview	
 • Outcome evaluation • Process evaluation /Implementation quality 	
 • 8-10 participants from intervention arm • 8-10 participants from control arm 	
 • At 6-7 months, Research coordinator will collect interview feedback post intervention 	
 • Barriers and facilitators • Wellbeing • Participant experiences • Suggestions for improvement • Planning for sustainability • Implementation quality 	
 • Interview questions
ICES provincial administrative database	
 • Outcome evaluation 	
 • up to 154 participants (77 per arm) (data linkage using OHIP#) 	
 • At 6-7 months, Study coordinator and Assistant will use OHIP number to link administrative data 	
 • Vaccine status • Rates of SARS-CoV-2 infection • Hospitalization • Death 	
 • ICES provincial administrative database fields

18b. Retention

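### Section 20a compares all outcomes by t-test, which gives no result for yes/no secondary outcomes without events and can disagree with methods for proportions when events are few

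*Combined protocol and SAP*

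**What the plan says.** Section 20a (Outcomes) has a reporting step and a comparison step. The first is "We will use descriptive statistics to report participant demographics and study outcomes". The second is "We will use t-tests to compare outcomes for the intervention and control groups". The comparison step does not separate scale outcomes from yes/no outcomes.

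Section 20b adds nothing: "There is no additional analysis that has been identified for this research study". Section 20c mentions the t-test again and adds only the qualitative analysis. No test for proportions, interval method, model or rule for sparse events appears anywhere in the document.

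Section 12 lists what the rule must cover: "Secondary outcome measures will include burnout, knowledge, access to and use of wellness supports, vaccination status, SARS-CoV-2 infection, hospitalization, and death". It later describes the data to be obtained by linkage as "vaccine status, and rates of SARS-CoV-2 infection, hospitalization and death, over the study period". No section states how these outcomes will be coded. One indicator per participant is the natural reading.

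**The concern.** A two-sample t-test divides the difference in means by a standard error built from the within-arm variances. For a 0/1 outcome, an arm with no events has zero variance, as does an arm in which everyone has the event. If both arms are empty or both are full, numerator and denominator are both zero and the planned comparison returns nothing. This could happen for a rare outcome such as death. It could also happen for vaccination status if every participant is vaccinated.

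A second difficulty arises with a few events. The t-test then returns a p-value, but one that can fall on the other side of 5% from methods built for proportions. No such method is named in advance, so the choice could be made after the counts are known.

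What is at stake is a clean, prespecified comparison for up to four secondary outcomes. The trial's main conclusion is not at stake.

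**Working it through.** **Inputs from the documents.** Section 14 gives 64 per arm before the attrition buffer and 77 per arm planned. Its 64 reproduces: effect size 0.5, two-sided 5%, power 80% and a t-test give 63.77, rounded up to 64. The buffered figure is 64 × 1.2 = 76.8, so 77. That calculation concerns the primary outcome. Here 77 and 64 serve only as a planned and an illustrative smaller arm size.

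**Assumed input.** The event rate p over the study period, taken as equal in both arms. The documents give none, so a range is shown.

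**1. No events in either arm.** With 0/77 v 0/77 both sample variances are 0, so t = 0/0. Software returns a missing value for the pooled and the Welch versions, and also for 77/77 v 77/77. A single event is enough to give a result: 0 v 1 of 77 gives |t| = 1.0, p = 0.32.

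**2. How likely that is.** P(undefined) = (1 − p)^(2n) + p^(2n). For example, at p = 1% and n = 77, 0.99^154 = 0.213; the second term is negligible.

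| Assumed rate | 77 per arm | 64 per arm |
|---|---|---|
| 0.5% | 46% | 53% |
| 1% | 21% | 28% |
| 2% | 4.5% | 7.5% |
| 3% | 0.9% | 2.0% |
| 5% | 0.04% | 0.14% |

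**3. Few events: 0 v 4 of 77.**
- t-test: difference 4/77 = 0.0519. Variance in the arm with events is 4 × 73 / (77 × 76) = 0.0499. Standard error is √(0.0499/77) = 0.0255. So |t| = 2.04 on 152 degrees of freedom, p = 0.043.
- Fisher's exact test: 2 × (77 × 76 × 75 × 74) / (154 × 153 × 152 × 151) = 2 × 0.0601 = 0.12.
- Newcombe 95% interval: the Wilson limits are 0 to 4.75% for 0/77 and 2.04% to 12.61% for 4/77. Lower limit: −5.19 − (12.61 − 5.19) = −12.6 points. Upper limit: −5.19 + √(4.75² + (5.19 − 2.04)²) = −5.19 + 5.70 = +0.5 points. The interval includes zero.

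**4. Size of the t-test over all possible counts.** Exact enumeration of two independent binomials, nominal two-sided 5%, equal rates:

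| Assumed rate | 77 per arm | 64 per arm |
|---|---|---|
| 1% | 0.7% | 0.4% |
| 2% | 3.0% | 2.2% |
| 5% | 4.2% | 4.7% |
| 10% | 4.8% | 5.1% |
| 50% | 4.4% | 4.3% |
| 90% | 4.8% | 5.1% |
| 95% | 4.2% | 4.7% |

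**5. What an interval gives when the t-test gives nothing.** For 0/n the Wilson upper limit is z²/(n + z²), with z² = 3.84. This is 3.84/80.84 = 4.75% at n = 77 and 3.84/67.84 = 5.66% at n = 64. The Newcombe interval for 0 v 0 is therefore about ±4.8 points and ±5.7 points.

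**The case against.** The strongest reply is that little is lost when the t-test fails. With 0 v 0 events no test can show a difference (Fisher p = 1), and the useful content is the pair of counts, which Section 20a already provides through descriptive statistics. This stands. A reader might infer that the protocol leaves nothing to report for such an outcome; it does not. What a prespecified interval adds is a statement of how large a difference the empty counts still allow.

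It can also be said that the t-test works well enough on 0/1 data. Over most of the range this stands too. A reader might infer from 0 v 4 that t-tests on yes/no outcomes are invalid, or that they inflate false positives. The calculations do not support this: the test is conservative at rates of 1% and 2% and close to nominal from about 5% to 95%. Disagreement is also confined to narrow patterns of counts. At 0 v 5 of 77 the t-test (p = 0.023) and Fisher (p = 0.058) differ, but the Newcombe interval sides with the t-test: Wilson limits for 5/77 are 2.81% to 14.32%, so the upper limit is −6.49 + √(4.75² + (6.49 − 2.81)²) = −0.5 points. With equal rates of 1% to 10%, the t-test and the Newcombe interval reach different decisions in at most about 2% of trials.

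Finally, the size of the problem rests on assumed rates. That death is the outcome most exposed is plausible, but the documents do not establish it.

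**Conclusion.** The point holds and is minor. The only between-arm method named is undefined for a yes/no outcome with no events in either arm (or with events in everyone), and with a few events it can cross 5% where methods for proportions do not. Under equal assumed rates, failure is about as likely as not at 0.5%, roughly one in four or five at 1%, and negligible at 5%. These figures also assume one yes/no indicator per participant and 77 or 64 participants per arm with data. Section 26a makes supplying the OHIP number a participant's choice, so the linked number may be smaller, which would make zero events more likely.

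A failure of the 0/0 kind would be visible and would not create a false conclusion. The primary outcome and the sample size are untouched.

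The document is also inconsistent about the source of these outcomes: the Research Question and part of Section 12 point to self-report and surveys, whereas a later part of Section 12 and Table 1 in Section 18a use ICES linkage. A reader might count this as part of the same defect. It does not cause the 0/0 failure and should be raised as a separate point.

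**What to change.** In Section 20a, limit t-tests to scale outcomes. For vaccination status, infection, hospitalization and death, state that n/N per arm and the risk difference with a score-based 95% confidence interval (Newcombe or Miettinen-Nurminen) will be reported, with no t-test.

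The cost is one or two sentences and a few lines of code, with no change to the sample size. The downside is that the interval is conservative at very low counts: at 77 per arm and equal rates, Newcombe coverage is about 99.9% at 1%, 99.1% at 2% and 96.6% at 5%. For outcomes at 5% or more, the change will rarely alter a conclusion. The gain there is one uniform prespecified method, reported as an effect with its uncertainty.

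N cannot be fixed until the data source for these outcomes is settled under the separate point.
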